9.3. Institutional Review Board (IRB)/Independent Ethics Committee (IEC)

It is the responsibility of the investigator to have prospective approval of the study protocol, protocol amendments, and informed consent forms, and other relevant documents, (eg, recruitment advertisements), if applicable, from the IRB/IEC. All correspondence with the IRB/IEC should be retained in the Investigator File. Copies of IRB/IEC approvals should be forwarded to Pfizer.

9.4. Ethical Conduct of the Study

The study will be conducted in accordance with legal and regulatory requirements, as well as with scientific purpose, value and rigor and follow generally accepted research practices described in Guidelines for Good Pharmacoepidemiology Practices (GPP) issued by the International Society for Pharmacoepidemiology (ISPE), Good Epidemiological Practice (GEP) guidelines issued by the International Epidemiological Association (IEA), Good Practices for Outcomes Research issued by the International Society for Pharmacoeconomics and Outcomes Research (ISPOR), International Ethical Guidelines for Epidemiological Research issued by the Council for International Organizations of Medical Sciences (CIOMS), European Medicines Agency (EMA) European Network of Centres for Pharmacoepidemiology and Pharmacovigilance (ENCePP) Guide on Methodological Standards in Pharmacoepidemiology, and FDA Guidance for Industry: Good Pharmacovigilance and Pharmacoepidemiologic Assessment, FDA Guidance for Industry and FDA Staff: Best Practices for Conducting and Reporting of Pharmacoepidemiologic Safety Studies Using Electronic Healthcare Data Sets, Guidance for Industry: Patient-Reported Outcome Measures: Use in Medical Product Development to Support Labeling Claims and/or equivalent.

10. MANAGEMENT AND REPORTING OF ADVERSE EVENTS/ADVERSE REACTIONS

10.1. Requirements

The table below summarizes the requirements for recording safety events on the case report form and for reporting safety events on the non-interventional study (NIS) adverse event monitoring (AEM) Report Form to Pfizer Safety. These requirements are delineated for three types of events: (1) serious adverse events (SAEs); (2) non-serious AEs (as applicable); and (3) scenarios involving drug exposure, including exposure during pregnancy, exposure during breast feeding, medication error, overdose, misuse, extravasation, and occupational exposure. These events are defined in the section “Definitions of safety events”.

Safety event	Recorded on the case report form	Reported on the NIS AEM Report Form to Pfizer Safety within 24 hours of awareness
SAE	All	All
Non-serious AE	All	None
Scenarios involving exposure to a drug under study, including exposure during pregnancy, exposure during breast feeding, medication error, overdose, misuse, extravasation; lack of efficacy; and occupational exposure	All (regardless of whether associated with an AE), except occupational exposure	All (regardless of whether associated with an AE)

For each AE, the investigator must pursue and obtain information adequate both to determine the outcome of the adverse event and to assess whether it meets the criteria for classification as a SAE (see section "Serious Adverse Events" below)

Safety events listed in the table above must be reported to Pfizer within 24 hours of awareness of the event by the investigator **regardless of whether the event is determined by the investigator to be related to a drug under study**. In particular, if the SAE is fatal or life-threatening, notification to Pfizer must be made immediately, irrespective of the extent of available event information. This timeframe also applies to additional new (follow-up) information on previously forwarded safety event reports. In the rare situation that the investigator does not become immediately aware of the occurrence of a safety event, the investigator must report the event within 24 hours after learning of it and document the time of his/her first awareness of the events.

For safety events that are considered serious or that are identified in the far right column of the table above that are reportable to Pfizer within 24 hours of awareness, the investigator is obligated to pursue and to provide any additional information to Pfizer in accordance with this 24-hour timeframe. In addition, an investigator may be requested by Pfizer to obtain specific follow-up information in an expedited fashion. This information is more detailed than that recorded on the case report form. In general, this will include a description of the adverse event in sufficient detail to allow for a complete medical assessment of the case and independent determination of possible causality. Any information relevant to the event, such as concomitant medications and illnesses must be provided. In the case of a patient death, a summary of available autopsy findings must be submitted as soon as possible to Pfizer or its designated representative.

10.1.1. Reporting Period

For each patient, the safety event reporting period begins at the time of the patient's first dose of Sunitinib or the time of the patient's informed consent if s/he is already exposed to Sunitinib, and lasts through the end of the observation period of the study, which must include at least 28 calendar days following the last administration of a drug under study; a report must be submitted to Pfizer Safety (or its designated representative) for any of the types of safety events listed in the table above occurring during this period. If a patient was administered a drug under study on the last day of the observation period, then the reporting period should be extended for 28 calendar days following the end of observation. Most often, the date of informed consent is the same as the date of enrollment. In some situations, there may be a lag between the dates of informed consent and enrollment. In these instances, if a patient provides informed consent but is never enrolled in the study (eg, patient changes his/her mind about participation, failed screening criteria), the reporting period ends on the date of the decision to not enroll the patient.

If the investigator becomes aware of a SAE occurring at any time after completion of the study and s/he considers the SAE to be related to sunitinib, the SAE also must be reported to Pfizer Safety.

10.1.2. Causality Assessment

The investigator is required to assess and record the causal relationship. For all AEs, sufficient information should be obtained by the investigator to determine the causality of each adverse event. For AEs with a causal relationship to sunitinib, follow-up by the investigator is required until the event and/or its sequelae resolve or stabilize at a level acceptable to the investigator, and Pfizer concurs with that assessment.

An investigator's causality assessment is the determination of whether there exists a reasonable possibility that sunitinib caused or contributed to an adverse event. If the investigator's final determination of causality is "unknown" and s/he cannot determine whether sunitinib caused the event, the safety event must be reported within 24 hours.

If the investigator cannot determine the etiology of the event but s/he determines that sunitinib did not cause the event, this should be clearly documented on the case report form and the NIS AEM Report Form.

10.2. Definitions of Safety Events

10.2.1. Adverse Events

An AE is any untoward medical occurrence in a patient administered a medicinal product. The event need not necessarily have a causal relationship with the product treatment or usage. Examples of adverse events include but are not limited to:

- Abnormal test findings (see below for circumstances in which an abnormal test finding constitutes an adverse event);
- Clinically significant symptoms and signs;
- Changes in physical examination findings;
- Hypersensitivity;
- Lack of efficacy;
- Drug abuse;
- Drug dependency.

Additionally, for medicinal products, they may include the signs or symptoms resulting from:

- Drug overdose;
- Drug withdrawal;
- Drug misuse;
- Off-label use;

- Drug interactions;
- Extravasation;
- Exposure during pregnancy;
- Exposure during breast feeding;
- Medication error;
- Occupational exposure.

Abnormal test findings

The criteria for determining whether an abnormal objective test finding should be reported as an adverse event are as follows:

- Test result is associated with accompanying symptoms, and/or
- Test result requires additional diagnostic testing or medical/surgical intervention, and/or
- Test result leads to a change in study dosing or discontinuation from the study, significant additional concomitant drug treatment, or other therapy, and/or
- Test result is considered to be an adverse event by the investigator or sponsor.

Merely repeating an abnormal test, in the absence of any of the above conditions, does not constitute an adverse event. Any abnormal test result that is determined to be an error does not require reporting as an adverse event.

10.2.2. Serious Adverse Events

A serious adverse event is any untoward medical occurrence in a patient administered a medicinal or nutritional product (including pediatric formulas) at any dose that:

- Results in death;
- Is life-threatening;
- Requires inpatient hospitalization or prolongation of hospitalization (see below for circumstances that do not constitute adverse events);
- Results in persistent or significant disability/incapacity (substantial disruption of the ability to conduct normal life functions);
- Results in congenital anomaly/birth defect.

Progression of the malignancy under study (including signs and symptoms of progression) should not be reported as a serious adverse event unless the outcome is fatal within the safety reporting period. Hospitalization due to signs and symptoms of disease progression should not be reported as a serious adverse event. If the malignancy has a fatal outcome during the study or within the safety reporting period, then the event leading to death must be recorded as an adverse event and as a serious adverse event with severity Grade 5.

Medical and scientific judgment is exercised in determining whether an event is an important medical event. An important medical event may not be immediately life-threatening and/or result in death or hospitalization. However, if it is determined that the event may jeopardize the patient or may require intervention to prevent one of the other outcomes listed in the definition above, the important medical event should be reported as serious.

Examples of such events are intensive treatment in an emergency room or at home for allergic bronchospasm; blood dyscrasias or convulsions that do not result in hospitalization; or development of drug dependency or drug abuse.

Additionally, any suspected transmission via a Pfizer product of an infectious agent, pathogenic or non-pathogenic, is considered serious. The event may be suspected from clinical symptoms or laboratory findings indicating an infection in a patient exposed to a Pfizer product. The terms “suspected transmission” and “transmission” are considered synonymous. These cases are considered unexpected and handled as serious expedited cases by PV personnel. Such cases are also considered for reporting as product defects, if appropriate.

10.2.3. Hospitalization

Hospitalization is defined as any initial admission (even if less than 24 hours) to a hospital or equivalent healthcare facility or any prolongation to an existing admission. Admission also includes transfer within the hospital to an acute/intensive care unit (eg, from the psychiatric wing to a medical floor, medical floor to a coronary care unit, neurological floor to a tuberculosis unit). An emergency room visit does not necessarily constitute a hospitalization; however, an event leading to an emergency room visit should be assessed for medical importance.

Hospitalization in the absence of a medical AE is not in itself an AE and is not reportable. For example, the following reports of hospitalization without a medical AE are not to be reported.

- Social admission (eg, patient has no place to sleep).
- Administrative admission (eg, for yearly exam).
- Optional admission not associated with a precipitating medical AE (eg, for elective cosmetic surgery).
- Hospitalization for observation without a medical AE.

- Admission for treatment of a pre-existing condition not associated with the development of a new AE or with a worsening of the pre-existing condition (eg, for work-up of persistent pre-treatment lab abnormality).
- Protocol-specified admission during clinical study (eg, for a procedure required by the study protocol).

10.2.4. Scenarios Necessitating Reporting to Pfizer Safety within 24 Hours

Scenarios involving exposure during pregnancy, exposure during breastfeeding, medication error, overdose, misuse, extravasation, lack of efficacy, and occupational exposure are described below.

Exposure during pregnancy

An exposure during pregnancy (EDP) occurs if:

1. A female becomes, or is found to be, pregnant either while receiving or having been exposed to (eg, environmental) sunitinib, or the female becomes, or is found to be, pregnant after discontinuing and/or being exposed to sunitinib (maternal exposure).

An example of environmental exposure would be a case involving direct contact with a Pfizer product in a pregnant woman (eg, a nurse reports that she is pregnant and has been exposed to chemotherapeutic products).

2. A male has been exposed, either due to treatment or environmental exposure to sunitinib prior to or around the time of conception and/or is exposed during the partner pregnancy (paternal exposure).

As a general rule, prospective and retrospective exposure during pregnancy reports from any source are reportable irrespective of the presence of an associated AE and the procedures for SAE reporting should be followed.

If a study participant or study participant's partner becomes, or is found to be, pregnant during the study participant's treatment with sunitinib, this information must be submitted to Pfizer, irrespective of whether an adverse event has occurred using the NIS AEM Report Form and the EDP Supplemental Form.

In addition, the information regarding environmental exposure to Sunitinib in a pregnant woman (eg, a subject reports that she is pregnant and has been exposed to a cytotoxic product by inhalation or spillage) must be submitted using the NIS AEM Report Form and the EDP supplemental form. This must be done irrespective of whether an AE has occurred.

Information submitted should include the anticipated date of delivery (see below for information related to termination of pregnancy).

Follow-up is conducted to obtain general information on the pregnancy; in addition, follow-up is conducted to obtain information on EDP outcome for all EDP reports with

pregnancy outcome unknown. A pregnancy is followed until completion or until pregnancy termination (eg, induced abortion) and Pfizer is notified of the outcome. This information is provided as a follow up to the initial EDP report. In the case of a live birth, the structural integrity of the neonate can be assessed at the time of birth. In the event of a termination, the reason(s) for termination should be specified and, if clinically possible, the structural integrity of the terminated fetus should be assessed by gross visual inspection (unless pre-procedure test findings are conclusive for a congenital anomaly and the findings are reported).

If the outcome of the pregnancy meets the criteria for an SAE (eg, ectopic pregnancy, spontaneous abortion, intrauterine fetal demise, neonatal death, or congenital anomaly [in a live born, a terminated fetus, an intrauterine fetal demise, or a neonatal death]), the procedures for reporting SAEs should be followed.

Additional information about pregnancy outcomes that are reported as SAEs follows:

- Spontaneous abortion includes miscarriage and missed abortion;
- Neonatal deaths that occur within 1 month of birth should be reported, without regard to causality, as SAEs. In addition, infant deaths after 1 month should be reported as SAEs when the investigator assesses the infant death as related or possibly related to exposure to investigational product

Additional information regarding the exposure during pregnancy may be requested. Further follow-up of birth outcomes will be handled on a case-by-case basis (eg, follow-up on preterm infants to identify developmental delays).

In the case of paternal exposure, the study participant will be provided with the Pregnant Partner Release of Information Form to deliver to his partner. It must be documented that the study participant was given this letter to provide to his partner.

For non-interventional studies conducted in pregnant women, data on the pregnancy outcome and non-serious AEs are expected to be collected and analyzed in the study database. In such instances, only EDPs associated with a SAE are to be reported.

Exposure during breastfeeding

Scenarios of exposure during breastfeeding must be reported, irrespective of the presence of an associated AE. An exposure during breastfeeding report is not created when a Pfizer drug specifically approved for use in breastfeeding women (eg, vitamins) is administered in accord with authorized use. However, if the infant experiences an AE associated with such a drug's administration, the AE is reported together with the exposure during breastfeeding.

Medication error

A medication error is any unintentional error in the prescribing, dispensing or administration of a medicinal product that may cause or lead to inappropriate medication use or patient harm

while in the control of the health care professional, patient, or consumer. Such events may be related to professional practice, health care products, procedures, and systems including: prescribing; order communication; product labeling, packaging, and nomenclature; compounding; dispensing; distribution; administration; education; monitoring; and use.

Medication errors include:

- Near misses, involving or not involving a patient directly (eg, inadvertent/erroneous administration, which is the accidental use of a product outside of labeling or prescription on the part of the healthcare provider or the patient/consumer);
- Confusion with regard to invented name (eg, trade name, brand name).

The investigator must submit the following medication errors to Pfizer, irrespective of the presence of an associated AE/SAE:

- Medication errors involving patient exposure to the product, whether or not the medication error is accompanied by an AE.
- Medication errors that do not involve a patient directly (eg, potential medication errors or near misses). When a medication error does not involve patient exposure to the product the following minimum criteria constitute a medication error report:
 - An identifiable reporter;
 - A suspect product;
 - The event medication error.

Overdose, Misuse, Extravasation

- Reports of overdose, misuse, and extravasation associated with the use of a Pfizer product are reported to Pfizer by the investigator, irrespective of the presence of an associated AE/SAE.

Lack of Efficacy

- Reports of lack of efficacy to a Pfizer product are reported to Pfizer by the investigator, irrespective of the presence of an associated AE/SAE or the indication for use of the Pfizer product.

Occupational Exposure

- Reports of occupational exposure to a Pfizer product are reported to Pfizer by the investigator, irrespective of the presence of an associated AE/SAE.

10.3. Single Reference Safety Document

The Sutent® Local Product Label approved by CFDA will serve as the single reference safety document during the course of the study, which will be used by Pfizer safety to assess any safety events reported to Pfizer Safety by the investigator during the course of this study.

The SRSD should be used by the investigator for prescribing purposes and guidance.

11. PLANS FOR DISSEMINATING AND COMMUNICATING STUDY RESULTS

Communication of Issues

In the event of any prohibition or restriction imposed (eg, clinical hold) by an applicable Competent Authority in any area of the world, or if the investigator is aware of any new information which might influence the evaluation of the benefits and risks of a Pfizer product, Pfizer should be informed immediately.

In addition, the investigator will inform Pfizer immediately of any urgent safety measures taken by the investigator to protect the study patients against any immediate hazard, and of any serious breaches of this NI study protocol that the investigator becomes aware of.

Regarding requirement from China Clinical Drug Evaluation(CDE), study progress and interim analysis result will be reported as following timeline.

Items	Planned date
Study annual report 1	16 November 2015
Study annual report 2	16 November 2016
Study interim analysis report 1	15 March 2017
Study annual report 3	15 November 2017
Study annual report 4	15 November 2018
Study annual report 5	13 November 2019
Study annual report 6	13 November 2020
Study annual report 7	15 November 2021
Study interim analysis report 2	TBD, upon renewal approval date
Study annual report 8	17 November 2022

13. LIST OF TABLES

None

14. LIST OF FIGURES

None

15. ANNEX 1. LIST OF STAND-ALONE DOCUMENTS

None

16. ANNEX 2. NATIONAL CANCER INSTITUTE (NCI) COMMON TERMINOLOGY CRITERIA FOR ADVERSE EVENTS (CTCAE)

Detail information of CTCAE 4.0 is described as below. Published: May 28, 2009 (v4.03: June 14, 2010):

<http://ctep.cancer.gov/reporting/ctc.html>

17. ANNEX 3. LABORATORY TESTS

	Conventional Units	Conversion Factor	SI Units
Hematology			
Hemoglobin (Hgb)	g/dL	x 10	g/L
Platelet count (Plt)	10 ³ /mm ³	x 10 ⁹	10 ¹² /L
White blood cell	10 ³ /mm ³	x 10 ⁶	10 ⁹ /L
Neutrophils (absolute)	10 ³ /mm ³	x 10 ⁶	10 ⁹ /L
Lymphocytes (absolute)	10 ³ /mm ³	x 10 ⁶	10 ⁹ /L
Chemistry			
Total bilirubin	mg/dL	x 17.1	μmol/L
Alanine transaminase (ALT)	U/L	N/A	U/L
Aspartate transaminase (AST)	U/L	N/A	U/L
Gamma-glutamyl transferase (GGT)	U/L	N/A	U/L
Alkaline phosphatase	U/L	N/A	U/L
Total protein	g/dL	x 10	g/L
Albumin	g/dL	x 10	g/L
Sodium	MEq/L	x 1.0	mmol/L
Potassium	MEq/L	x 1.0	mmol/L
Chloride	MEq/L	x 1.0	mmol/L
Calcium	mg/dL	x 0.25	mmol/L
Creatinine	mg/dL	x 88.4	μmol/L
Phosphorus	mg/dL	x 0.323	mmol/L
Uric acid	mg/dL	x 0.059	mmol/L
Blood urea nitrogen (BUN)/Urea	mg/dL	x 0.357	mmol/L
Creatinine	mg/dL	x 88.4	mol/L
Glucose	mg/dL	x 0.055	mmol/L
Thyroid function Tests			
Serum Thyrotropin (TSH)	μU/mL		
Free Triiodothyronine (T3)	pg/dL		
Free Thyroxine (T4)	ng/dL

1. AMENDMENTS FROM PREVIOUS VERSION(S)

Document	Version Date	Summary of Changes
Version 3	29 May 2018	
 • Changed from “Not applicable” to “Protocol deviations (minor/major) will be” in Section 5.6 on Page 8. • Added censoring rule for patients with documentation of a PFS event after an unacceptably long interval in Section 6.1.1 on Page 8. • Changed the window of censorship for patients died with no on-study disease assessments from “prior to the first planned assessment” to “within 17 weeks post first dose” in Section 6.1.1 on Page 8 and in Section 6.1.2 on Page 9. • Added definition for adequate baseline in Section 6.1.1 on Page 8. • Added censoring rule for patients with documentation of a PFS by clinical judgment event after an unacceptably long interval in Section 6.1.2 on Page 9. • Remove “Patients with inadequate baseline disease assessment are censored at the start date” in Section 6.1.2 on Page 9. • Added “Sensitivity analyses will be conducted for efficacy endpoints by excluding patients with major protocol deviations” in Section 8.2.2 on Page 11.
Version 2	08 June 2016	
 • Changed from “Eligible subjects...” to “The dosage of sunitinib...” in Section 2.1 on Page 5. • Added the “Variables” information from the study Protocol to the Section 2.1 on Page 5-6. • Defined the “default start date” on Page 7. • Deleted the duplicated definitions of “default start date” in Sections 6.1.1, 6.1.2, 6.1.3 and 6.1.4 on Page 7. • Added “All analyses....” in Section 8.1 on Page 10.

		• Deleted “see the list in Section 5.2” on Page 11.
Version 1	16 June 2014	Finalized

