8.7. Data Analysis

Detailed methodology for summary and statistical analyses of data collected in this study will be documented in a Statistical Analysis Plan (SAP), which will be dated, filed and maintained by the sponsor. The SAP may modify the plans outlined in the protocol; any major modifications of primary endpoint definitions or their analyses would be reflected in a protocol amendment.

The results of this study will be presented using descriptive statistics. The primary analysis will be performed on all subjects who receive at least one dose of sunitinib.

Data will be collected in a standard format electronic CRF as described in the Study Procedures (see 8.3 Variables).

All analyses will be performed on all subjects who receive at least one dose of Sunitinib.

Primary safety outcomes include the frequency of adverse events and serious adverse events. Adverse events of particular interest are as follows:

- Infections and infestations.
- Cardiac and vascular.
- Skin and subcutaneous tissue:
 - The most common skin and subcutaneous tissue related adverse events of interest are rash (includes erythematous, macular, or scaly rash), hand foot syndrome (HFS) or palmo plantar erythrodysesthesia (PPE), dry skin and skin discoloration.
- Gastrointestinal.
- Psychiatric and nervous system.

- Musculoskeletal.
- Thyroid function.
- General disorders.
- Others.
- laboratory abnormalities:
 - Haematologic: hemoglobin, platelet count, white blood cell count, neutrophile granulocyte count.
 - Non Haematologic: total bilirubin, ALT (Alanine Transaminase), AST (Aspartate Transaminase), alkaline phosphatase, GGT (Gamma-Glutamyl Transferase), total protein, albumin, BUN (Blood Urea Nitrogen), creatinine, uric acid, glucose, hypocalcemia, hyponatremia, hypophosphatemia, hypokalemia.

Secondary efficacy endpoints are the progression-free survival time, progression-free survival by clinical judgment, overall survival time and 5-year survival rate.

Progression-Free Survival is defined as the time from the start of sunitinib treatment to first documentation of objective tumor progression or to death due to any cause, whichever occurs first. PFS data will be censored on the date of the last tumor assessment on study for subjects who do not have objective tumor progression and who do not die while on study.

Default start date is date of first treatment, if this date is not available, date of enrollment will be used.

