3. INTERIM ANALYSES, FINAL ANALYSES AND UNBLINDING

Two interim analyses are planned to deliver interim reports to CDE before 15 Mar 2017 and some day in year 2022 for license renewal. The interim analyses will include all the data and analyses that will be reported in the final analysis.

Final analysis will be conducted after the official database is released.

Unblinding is not applicable for this study as it is a non-interventional single arm study, and no DMC is needed.

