6.1.1. Progression-Free Survival

Investigator assessed PFS according to RECIST 1.1. PFS is defined as the time from start date to first document of objective tumor progression or death due to any cause, whichever occurs first. PFS (in months) will be calculated as (first event date — start date +1)/30.44.

PFS data will be censored on the date of the last objective tumor assessment on study for subjects who do not have objective tumor progression and who do not die while on study. Patients with documentation of a PFS event after an unacceptably long interval (>17 weeks) since the previous objective disease assessment will be censored at the date of the previous assessment. Patients with no on-study objective disease assessments are censored at the start date unless death occurred within 17 weeks post first dose (in which case the death is an event). Patients with inadequate baseline disease assessment are censored at the start date. Adequate baseline is defined using the following criteria:

- Subjects with target lesions: All target lesions had measurement(s) within the baseline window (200 days) and measurable.
- Subjects with non-target lesions only: All non-target lesions had non missing assessments(s) and at least one of the non-target lesions assessed as non-indeterminate within the baseline window (200 days).

Additionally, subjects who start a new anti-cancer therapy prior to Progressive Disease (PD) will be censored at the date of the last tumor assessment prior to the start of the new therapy.

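### SAP Version 3 added a 17-week censoring rule to both PFS endpoints, without a stated reason and after the planned first interim, and no planned analysis shows PFS without it

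*SAP*

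**What the plan says.** **Timing.** SAP Section 3 states: "Two interim analyses are planned to deliver interim reports to CDE before 15 Mar 2017", with a second interim in 2022 for license renewal. On content it says: "The interim analyses will include all the data and analyses that will be reported in the final analysis". Both PFS endpoints therefore belong in interim report 1. Neither the Version 2 nor the Version 3 change list mentions Section 3, so this sentence appears to have been in force at that interim.

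**Change.** The Version 3 log has seven entries, and five concern PFS rules. Two add the long-interval rule. The entry for PFS reads: "Added censoring rule for patients with documentation of a PFS event after an unacceptably long interval in Section 6.1.1 on Page 8". Its counterpart for the second endpoint reads: "Added censoring rule for patients with documentation of a PFS by clinical judgment event after an unacceptably long interval in Section 6.1.2 on Page 9". The third alters the window for deaths without any assessment. The fourth reads: "Added definition for adequate baseline in Section 6.1.1 on Page 8". The fifth removes the inadequate-baseline censoring from PFS by clinical judgment. No entry carries a reason.

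**Current rule.** SAP 6.1.1 now addresses "Patients with documentation of a PFS event after an unacceptably long interval (>17 weeks) since the previous objective disease assessment" and censors those patients at the date of that previous assessment. SAP 6.1.2 does the same for PFS by clinical judgment. Death is a component of both endpoints, so late deaths fall under the rule as well.

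**Protocol.** Section 8.7 gives the basic rule: "PFS data will be censored on the date of the last tumor assessment on study for subjects who do not have objective tumor progression". Its sentence goes on to exempt deaths on study from this censoring. It sets no limit on the interval before an event and no condition on the baseline assessment. Section 8.3 says the protocol specifies no patient visits.

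**Sensitivity analyses.** SAP 8.2.2 plans one for efficacy, which excludes patients with major protocol deviations.

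**The concern.** A rule that decides which progressions and deaths count as events is best fixed before anyone can see what it does to the curve. This one is dated after a report that was planned to show the full PFS analyses, in a single-arm open study, and comes without a rationale. It also departs from the protocol in one direction: it takes events away and adds none.

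Imaging follows routine practice, and Protocol 8.9 names variable imaging timing as a limitation. Intervals above 17 weeks are therefore plausible, and the rule may act on a noticeable share of patients. The regulator is due interim report 1, a renewal interim and a final report. If the reported PFS lengthens between them, nothing planned would let a reader separate longer follow-up from the changed rule.

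**Working it through.** **1. Dates.** Interim 1 was planned for 15 March 2017 (SAP 3, Protocol 5); Version 3 is dated 29 May 2018.
- 15 March 2017 to 15 March 2018 is 365 days, and on to 29 May 2018 is 75 more: 365 + 75 = 440 days. 440 / 30.44 = 14.5 months.
- From the planned start of data collection, 15 December 2014, to Version 3: 1,261 days / 30.44 = 41.4 months.

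**2. Data expected by then.** Protocol 8.5 gives about 20 patients a year for five years: 20 x 5 = 100, which reproduces the stated size. At that rate, enrolment would be 20 x 821 / 365.25 = 45 patients at the planned interim and 20 x 1,261 / 365.25 = 69 at Version 3. These are planned figures, not actual ones.

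**3. Rules side by side.**

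| Situation | Protocol 8.7 | Current SAP 6.1.1 / 6.1.2 |
|---|---|---|
| Progression more than 17 weeks after previous assessment | Event | Censored at previous assessment |
| Death more than 17 weeks after previous assessment | Event | Censored at previous assessment |
| No assessment after start of treatment | Censored at start | Censored at start, unless death within 17 weeks of first dose |
| Inadequate baseline | No rule | PFS: censored at start. PFS by clinical judgment: no rule |
| New anti-cancer therapy before progression | Censored at last prior assessment | Same |

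The first two rows contain the substantive new rule.

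**4. Direction.** The rule turns some events into earlier censorings and never the reverse. Dropping an event removes a downward step from the Kaplan-Meier curve, so the usual effect is a longer median. This is a tendency, not a certainty in every sample, because the patient also leaves the risk set early. Take five patients with events at 1, 2, 3, 10 and 11 months, the last two scanned only at 0.5 months. Without the rule the curve runs 0.80, 0.60, 0.40, so the median is 3 months. With the rule, those two are censored at 0.5, three remain at risk, the curve runs 0.67, 0.33, and the median is 2 months. Such reversals need very long gaps in a small sample; in the simulation below no median fell.

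**5. Size, by illustration only.** The limit is 17 x 7 / 30.44 = 3.9 months. The documents give no scan intervals. Protocol 8.2.2 says only that visits are usually every 1 or 2 months. The simulation assumes exponential PFS with a median of 11.4 months (the Phase 3 sunitinib arm cited in Protocol 6), 15% of events being deaths, log-normal scan gaps, 60 months of follow-up and 20,000 simulated patients per row.

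| Median scan gap | Log-SD of gaps | Events turned into censorings | KM median without rule | KM median with rule |
|---|---|---|---|---|
| 2 months | 0.2 | 0% | 12.3 | 12.3 |
| 2 months | 0.6 | 25% | 13.0 | 15.2 |
| 3 months | 0.2 | 10% | 13.0 | 14.0 |
| 3 months | 0.6 | 48% | 13.8 | 20.7 |
| 4 months | 0.2 | 53% | 13.3 | 23.5 |
| 4 months | 0.6 | 64% | 14.6 | 28.0 |

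Medians are in months. They exceed 11.4 even without the rule because progression is dated at the scan that finds it. The ratio of medians runs from 12.3 / 12.3 = 1.0 to 28.0 / 14.6 = 1.9.

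**The case against.** A reader might infer that the PFS rules were rewritten in the light of the interim results. The documents do not support that. The interim date and content are plans; nothing shows when the report was issued, how many PFS events it held, or whether those who drafted Version 3 used it. Nor does the log list any change to the event definitions, to censoring at the last assessment or to censoring at new therapy.

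Three of the five PFS entries have an innocent reading:
- The entry beginning "Changed the window of censorship for patients died with no on-study disease assessments from" replaces a reference to the first planned assessment, which cannot be dated when the protocol plans no visits.
- The adequate-baseline entry supplies a definition; the log does not list the PFS baseline rule itself as new.
- Dropping the baseline condition from PFS by clinical judgment moves the SAP closer to Protocol 8.7, which has none.

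The long-interval rule also has an intelligible purpose: it avoids using a progression date that is poorly located after a long gap. That argument is weaker for deaths, whose dates do not depend on scans.

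On consequences, the study is descriptive with no decision rules, and PFS is secondary. Protocol 8.7 lets the SAP modify its plans and calls for an amendment only for major changes to the primary endpoint. No comparison of interim 1 with the final is planned. The simulation rests on assumed scan gaps and cannot establish the actual shift.

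All of this stands and limits the weight of the point. It leaves open that the 17-week rule is new, unexplained, absent from the protocol and not tested by any planned analysis.

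**Conclusion.** The point holds as a gap in the plan's sensitivity analyses and documentation. It is neither a finding of result-driven analysis nor a procedural breach. No type I error is at stake.

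The rule's expected effect is to leave the PFS median unchanged or lengthen it. Its size in this cohort is unknown: under the stated assumptions it runs from nil, with regular 2-month scans, to about 1.9 times, with irregular 4-month scans. That range is wide enough to justify showing PFS with and without the rule. The timing statement rests on planned dates and on SAP Section 3 having read the same at interim 1. The Version 2 text is not available beyond what the log quotes.

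**What to change.** In SAP 8.2.2, add a sensitivity analysis of PFS and PFS by clinical judgment at interim 2 and the final under the protocol 8.7 censoring rules, with no 17-week rule and no baseline-adequacy exclusion. Present it beside the Version 3 analysis. With it:
- Report the number of events reclassified by the 17-week rule (progressions and deaths separately), by the window for unassessed deaths, and by the baseline rule.
- State that the Version 3 rules were set after the planned interim 1 date, why, and whether interim PFS results were known at the time.
- Base any comparison with the 2017 interim on the rules actually programmed for that interim. Protocol 8.7 and the pre-Version 3 SAP are not one rule set: the log shows that the SAP already had a death window and a baseline exclusion that 8.7 lacks.

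The cost is one further run, a short SAP addition and a second median for each PFS endpoint in the report.
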